11.0 Posting of Survey Information

Takeda Pharmaceutical Company Limited will post survey information on Clinical Trials.gov and an open website (JAPIC-CTI*) before starting the survey.

* Japan Pharmaceutical Information Center-Clinical Trials Information

14.0 Other Necessary Matters

14.1 Revision of the Protocol

[figure not shown]
[figure not shown]
[figure not shown]
[figure not shown]
[figure not shown]
[figure not shown]
[figure not shown]
[figure not shown]
[figure not shown]
During the survey, attention will be paid to comprehend the status of progression of the survey, presence or absence of unexpected adverse drug reactions (ADRs)/serious ADRs (based on precautions), presence or absence of increased incidence of certain ADRs, and appropriateness of survey items, and this protocol will be reviewed and revised if necessary. If partial change to dosage and administration or indications is approved during the survey, the necessity of revising the protocol will be discussed if necessary, and the protocol will be revised as needed.

14.2 Actions to be Taken for Problems and Questions

If any safety or efficacy problem is detected, data will be carefully examined to discuss measures.

Appendix Observation schedule

Time point of survey		Observation period														
Survey item		At patient registration	Start of treatment	After 1 month of treatment	After 2 months of treatment	After 3 months of treatment	After 4 months of treatment	After 5 months of treatment	After 6 months of treatment	After 7 months of treatment	After 8 months of treatment	After 9 months of treatment	After 10 months of treatment	After 11 months of treatment	After 12 months of treatment	At discontinuation of treatment
Patient registration	Date of prescription of Zacras Combination Tablets	○														
	Patient identification number	○														
	Patient initials	○														
	Sex	○														
	Date of birth	○														
	Inclusion/exclusion criteria	○														
	Presence or absence of breast-feeding (only females)	○														
	Time of diagnosis of hypertension		○													
Patient demographics and baseline characteristics	Diagnostic category		○													
	Predisposition to hypersensitivity		○													
	Concurrent illness		○													
	Medical history		○													
	Height, body weight		○													
	Smoking history		○													
	Drinking history		○													
	Presence or absence of breast-feeding (only females)		○													
	Details on the use of Zacras Combination Tablets			↔	○	↔								○		
	Details on the use of other antihypertensive			↔	○	↔								○		
Treatment given, etc.	Details on the use of concomitant non-antihypertensive drug			↔	○	↔								○		
	Office blood pressure	○	○	○	○	○	○	○	○	○	○	○	○	○	○	
	Pulse rate	○	○	○	○	○	○	○	○	○	○	○	○	○	○	
	White blood cell count			↔	○	↔									○	
	Platelet count			↔	○	↔									○	
	AST			↔	○	↔									○	
Tests/observations, etc.	ALT			↔	○	↔									○	

γ -GTP		
Serum creatinine		
BUN		
Serum potassium		
Presence or absence of pregnancy (only females)		
Adverse event		

○ : Performed

← ○ →: Performed throughout the period

1.0 Definitions of Terms, etc. and Handling of Test/Measurement Data

1.1 Definitions

Term	Definition
Zacras	Zacras Combination Tablets are abbreviated as Zacras in this document.
SOC	System organ class listed in the MedDRA/J
HLGT	High level group term listed in the MedDRA/J
PT	Preferred term listed in the MedDRA/J
LLT	Lowest level term listed in the MedDRA/J
Enrolled patient	Patient allowed to be enrolled
Patient from whom the CRF is collected	Patient from whom the CRF has been obtained
Patient from whom the CRF is not collected	Enrolled patient from whom the CRF has not been collected
Finalized patient	Patient from whom the CRF is collected who has the date of CRF completion entered into the PMS system or who requires no information on the CRF status and has not been excluded from the survey
Non-finalized patient	Patient from whom the CRF is collected who has not been finalized
Patient included in safety evaluation	Finalized patient who is included in safety evaluation
Patient excluded from safety evaluation	Finalized patient who is excluded from safety evaluation
Patient included in efficacy evaluation	Patient included in safety evaluation who is included in efficacy evaluation
Patient excluded from efficacy evaluation	Patient included in safety evaluation who is excluded from safety evaluation
Presence or absence of change in daily dose of Zacras	“Yes” for patients with a change in daily dose between the start of treatment with Zacras and the final assessment
Duration of treatment with Zacras	End date of treatment with Zacras - start date of treatment with Zacras + 1
End date of treatment	End date of the final dose described in the column of the end date of treatment in the CRF; or start date of treatment + 360 days if the end date of treatment is not described in the CRF and there is a check for “ongoing at 12 months after the start of treatment with Zacras.”
Treatment completer	Patient with a duration of treatment with Zacras of \geq start date of treatment + 360 days
Treatment non-completer	Patient with a duration of treatment with Zacras of \leq start date of treatment +

Term	Definition
	359 days
Reason for discontinuation of treatment with Zacras	
If the duration of treatment with Zacras is \leq start date of treatment + 359 days, the reason for discontinuation of treatment described in the column of details on the use of Zacras in the CRF will be employed.
 
If the duration of treatment with Zacras is \geq start date of treatment + 360 days, the patient will be handled as a treatment completer; therefore, the reason for discontinuation of treatment described in the column of details on the use of Zacras in the CRF will not be employed.

Azilsartan and amlodipine besilate (hereinafter referred to as amlodipine) used before the start of treatment with Zacras	
Antihypertensives other than Zacras that are terminated on the start day of treatment with Zacras or the previous day. Antihypertensives other than Zacras will be classified as described below based on the ingredients and their doses listed below. Fixed-dose combinations will also be classified based on individual ingredients and their doses.
 
Azilsartan 20 mg, amlodipine 2.5 mg, amlodipine 5 mg, combined use of azilsartan 20 mg/amlodipine 2.5 mg, combined use of azilsartan 20 mg/amlodipine 5 mg, other

Switching to Zacras (by ingredient/dose)	
Switching to Zacras will be classified as described below based on the combination of “azilsartan and amlodipine used before the start of treatment with Zacras” and “initial dose of Zacras.”
 
Azilsartan 20 mg→Zacras LD, azilsartan 20 mg→Zacras HD, amlodipine 2.5 mg→Zacras LD, amlodipine 5 mg→Zacras HD, combined use of azilsartan 20 mg/amlodipine 2.5 mg→Zacras LD, combined use of azilsartan 20 mg/amlodipine 5 mg→Zacras HD, other

Switching to Zacras (by ingredient)	
Switching to Zacras will be classified as described below based on “switching to Zacras (by ingredient/dose).”
 
“Azilsartan→Zacras” for “azilsartan 20 mg→Zacras LD” or “azilsartan 20 mg→Zacras HD”
 
“Amlodipine→Zacras” for “amlodipine 2.5 mg→Zacras LD” or “amlodipine 5 mg→Zacras HD”
 
“Combined use of azilsartan/amlodipine→Zacras” for “combined use of azilsartan 20 mg/amlodipine 2.5 mg→Zacras LD” or “combined use of azilsartan 20 mg/amlodipine 5 mg→Zacras HD”
 
“Other” for “other”

Patient who switches from combined use	Patient with “combined use of azilsartan/amlodipine→Zacras” for switching to Zacras (by ingredient)

Term	Definition
Duration of disease	(Start date of treatment with Zacras - time of diagnosis of hypertension + 1) $\div 365.25$. For time of diagnosis of hypertension, 1 will be used as the day, and January 1 will be used if the month is unknown. The duration of disease will be handled as missing if the year, month, and day are unknown.
ADR, etc.	Abbreviation of “adverse drug reaction/infection” AE other than those assessed by the investigator to be not related to Zacras In this document, “adverse drug reaction/infection” is used in titles, and “adverse drug reaction, etc.” is used in the text and tables.
SAE	Adverse event assessed by the investigator to be serious Events included in the MedDRA code list in Takeda Medically Significant AE List will be handled as serious even if assessed by the investigator to be non-serious.
Number of patients with an AE or an ADR, etc.	Number of patients who experienced an AE or an ADR, etc.
Number of AE or ADR, etc.	Number of reported AE or ADR, etc.
Time of onset	Time of onset will be calculated as date of onset of AE (or ADR, etc.) - start date of treatment + 1. If the month and day of AE (or ADR, etc.) are unknown, January 1 will be used for calculation. If an AE (or ADR, etc.) occurs in the same year as treatment is started, the month and day of starting treatment will be used for calculation. If the day of AE (or ADR, etc.) is unknown, 1 will be used for calculation. If an AE (or ADR, etc.) occurs in the same year and month as treatment is started, the start date of treatment will be used for calculation. If the year, month, and day of AE (or ADR, etc.) is unknown, the start date of treatment will be used for calculation.
Patient with concurrent diabetes	Patient with a check for diabetes in the column of concurrent illness in the CRF or concurrent illness corresponding to Standardised MedDRA query (hereinafter referred to as SMQ) code 20000041 (hyperglycaemia/new onset diabetes mellitus SMQ [scope: narrow]) described
Patient with concurrent dyslipidemia	Patient with a check for dyslipidemia in the column of concurrent illness in the CRF or concurrent illness corresponding to SMQ code 20000026 (dyslipidaemia SMQ [scope: narrow]) described
Patient with concurrent hyperuricemia	Patient with a check for hyperuricemia in the column of concurrent illness in the CRF or concurrent illness corresponding to MedDRA PT code 10020903 (hyperuricaemia) described

Term	Definition
Patient with concurrent cardiac failure	Patient with a check for cardiac failure in the column of concurrent illness in the CRF or concurrent illness corresponding to SMQ code 20000004 (cardiac failure SMQ [scope: narrow]) described in the column of other disease: name of disease
Patient with concurrent coronary artery disease	Patient with a check for myocardial infarction or angina in the column of concurrent illness in the CRF, concurrent illness corresponding to SMQ code 20000043 (ischaemic heart disease SMQ [scope: narrow]) described in the column of other disease: name of disease, or PT corresponding to SMQ code 20000047 (myocardial infarction SMQ [scope: narrow]) described in the column of medical history
Patient with concurrent myocardial infarction (including old myocardial infarction)	Patient with a check for myocardial infarction in the column of concurrent illness in the CRF or PT corresponding to SMQ code 20000047 (myocardial infarction SMQ [scope: narrow]) described in the column of other disease: name of disease or medical history
Patient with concurrent angina	Patient with a check for angina in the column of concurrent illness in the CRF or concurrent illness corresponding to MedDRA PT code 10002383 (angina pectoris), 10002388 (angina unstable), 10036759 (Prinzmetal angina), or 10058144 (postinfarction angina) described in the column of other disease: name of disease
Patient with concurrent coronary artery disease (other)	Patient with concurrent coronary artery disease who is not a patient with concurrent myocardial infarction (including old myocardial infarction) or angina
Patient with concurrent atrial fibrillation	Patient with a check for atrial fibrillation in the column of concurrent illness in the CRF or concurrent illness corresponding to MedDRA PT code 10003658 (atrial fibrillation) described in the column of other disease: name of disease
Patient with concurrent renal impairment	Patient with a check for chronic kidney disease (CKD), diabetic nephropathy, nephrosclerosis, or other in the column of concurrent illness in the CRF or concurrent illness corresponding to the following (1), (2), or (3) described in the column of other disease: name of disease: (1) SMQ code 20000213 (chronic kidney disease SMQ [scope: narrow]) (2) Takeda MedDRA query (hereinafter referred to as TMQ) (Renal Disease) (3) TMQ (Renal Impairment)
Patient with concurrent chronic kidney disease	Patient with a check for chronic kidney disease (CKD), diabetic nephropathy, nephrosclerosis, or other in the column of concurrent illness in the CRF or

Term	Definition
(CKD)	concurrent illness corresponding to SMQ code 20000213 (chronic kidney disease SMQ [scope: narrow]) described in the column of other disease: name of disease
Patient with concurrent diabetic nephropathy	Patient with a check for diabetic nephropathy in the column of concurrent illness in the CRF or concurrent illness corresponding to MedDRA PT code 10061835 (diabetic nephropathy) described in the column of other disease: name of disease
Patient with concurrent nephrosclerosis	Patient with a check for nephrosclerosis in the column of concurrent illness in the CRF or concurrent illness corresponding to MedDRA PT code 10029159 (nephrosclerosis) described in the column of other disease: name of disease
Patient with concurrent chronic kidney disease (CKD) (other)	Patient with concurrent chronic kidney disease (CKD) who is not a patient with concurrent diabetic nephropathy or nephrosclerosis
Patient with concurrent renal impairment (other)	Patient with concurrent renal impairment who is not a patient with concurrent chronic kidney disease (CKD), diabetic nephropathy, nephrosclerosis, or chronic kidney disease (CKD) (other)
Patient with concurrent hepatic impairment	Patient with a check for hepatic steatosis or alcoholic hepatopathy in the column of concurrent illness in the CRF or concurrent illness corresponding to the following (1), (2), or (3) described in the column of other disease: name of disease: (1) SMQ code 20000005 (hepatic disorders SMQ [scope: narrow]) (2) MedDRA PT code 10019708 (hepatic steatosis) MedDRA PT code 10001627 (alcoholic liver disease)
Patient with concurrent hepatic steatosis	Patient with a check for hepatic steatosis in the column of concurrent illness in the CRF or concurrent illness corresponding to MedDRA PT code 10019708 (hepatic steatosis) described in the column of other disease: name of disease
Patient with concurrent alcoholic hepatopathy	Patient with a check for alcoholic hepatopathy in the column of concurrent illness in the CRF or concurrent illness corresponding to MedDRA PT code 10001627 (alcoholic liver disease) described in the column of other disease: name of disease
Patient with concurrent hepatic impairment (other)	Patient with concurrent hepatic impairment who is not a patient with concurrent hepatic steatosis or alcoholic hepatopathy
Patient with concurrent cerebrovascular disorder	Patient with PT corresponding to SMQ code 20000060 (cerebrovascular disorders SMQ [scope: narrow]) described in the column of concurrent

Term	Definition
	illness: other disease: name of disease or medical history in the CRF
Age	If the month and day of starting treatment is smaller than the month and day of birth, age will be calculated as year of starting treatment - year of birth - 1. If the month and day of starting treatment is equal to or greater than the month and day of birth, age will be calculated as year of starting treatment - year of birth. If the month and day of birth is unknown, January 1 will be used for calculation. If the day of birth is unknown, 1 will be used for calculation.
Young, middle-aged, or young-old patient	Patient aged 15 years or older and 74 years or younger
Old-old patient	Patient aged 75 years or older
BMI	BMI will be calculated as body weight (kg) / [0.0001 × height (cm) × height (cm)]. BMI will be displayed to one decimal place by rounding.
Concomitant drug (at the start of treatment with Zacras)	Concomitant drug that is started before the start of treatment with Zacras and is not terminated on the day before the start of treatment with Zacras, or concomitant drug that is started on the start day of treatment with Zacras
Concomitant drug (during the survey period)	Concomitant drug used during a period from the start day of treatment with Zacras to the end day of treatment with Zacras
Concomitant drug (at the end of treatment with Zacras)	Concomitant drug used on the end day of treatment with Zacras
Antihypertensive used within 2 months before the start of treatment with Zacras	Drug described in the column for details on the use of other antihypertensive in the CRF that is started before the start day of treatment with Zacras and used within 2 months (60 days) before the start of treatment with Zacras (excluding drugs that are started on the start day of treatment with Zacras)
Antidiabetic	Drugs with a NHI drug code starting with 396, 2492, or 249941
Antidyslipidemic	Drugs with a NHI drug code starting with 218 or any of the following 7-digit numbers: 2190101, 2190102, 2190103, 2190104
Antihyperuricemic	Drugs with a NHI drug code starting with 394
Antihypertensive	ACE inhibitors, angiotensin receptor blockers (ARBs), diuretics (thiazide and thiazide analogue diuretics), calcium antagonists (hereinafter referred to as Ca antagonists), direct renin inhibitors, aldosterone antagonists/potassium-sparing diuretics, vasodilators, β -blockers, central sympathetic inhibitors, $\alpha\beta$ -blockers, α_1 -blockers, fixed-dose combination: ARB + diuretic, fixed-dose combination: ARB + Ca antagonist, fixed-dose

Term	Definition
	combination: Ca antagonist + statin, and fixed-dose combination: ARB + Ca antagonist + diuretic in a list of antihypertensives in the Guidelines for the Management of Hypertension 2014 (JSH2014)
ACE inhibitor	
Drugs described in the column for details on the use of other antihypertensive in the CRF that have a NHI drug code starting with the following 4-digit number:
 
2144
 
Generic name: captopril, enalapril maleate, perindopril erbumine, lisinopril hydrate, alacepril, delapril hydrochloride, benazepril hydrochloride, cilazapril hydrate, imidapril hydrochloride, temocapril hydrochloride, quinapril hydrochloride, trandolapril

ARB	
Drugs described in the column for details on the use of other antihypertensive in the CRF that have a NHI drug code starting with any of the following 7-digit numbers:
 
2149039, 2149040, 2149041, 2149042, 2149044, 2149046, 2149048, 2149110, 2149111, 2149112, 2149113, 2149119, 2149116, 2149114, 2149117, 2149118, 2149115, 2149120, 2149122
 
Generic name: losartan potassium, candesartan cilexetil, valsartan, telmisartan, olmesartan medoxomil, irbesartan, azilsartan, losartan potassium/hydrochlorothiazide, candesartan cilexetil/hydrochlorothiazide, valsartan/hydrochlorothiazide, telmisartan/hydrochlorothiazide, irbesartan/trichlormethiazide, candesartan cilexetil/amlodipine besilate, valsartan/amlodipine besilate, telmisartan/amlodipine besilate, irbesartan/amlodipine besilate, olmesartan medoxomil/azelnidipine, valsartan/cilnidipine, azilsartan/amlodipine besilate, telmisartan/amlodipine besilate/hydrochlorothiazide

Diuretic (thiazide and thiazide analogue diuretic)	
Drugs described in the column for details on the use of other antihypertensive in the CRF that have a NHI drug code starting with any of the following 7-digit numbers:
 
2132003, 2132004, 2132006, 2149103, 2149012, 2135001, 2149007, 2149003, 2149110, 2149111, 2149112, 2149113, 2149119, 2149122
 
Generic name: trichlormethiazide, hydrochlorothiazide, benzylhydrochlorothiazide, indapamide, mefruside, tripamide, meticrane, losartan potassium/hydrochlorothiazide, candesartan cilexetil/hydrochlorothiazide, telmisartan/hydrochlorothiazide, valsartan/hydrochlorothiazide, irbesartan/trichlormethiazide, telmisartan/amlodipine besilate/hydrochlorothiazide

Term	Definition
HCTZ	
Drugs described in the column for details on the use of other antihypertensive in the CRF that have a NHI drug code starting with any of the following 7-digit numbers:
 
2132004, 2149110, 2149111, 2149112, 2149113, 2149122
 
Generic name: hydrochlorothiazide, losartan potassium/hydrochlorothiazide, candesartan cilexetil/hydrochlorothiazide, valsartan/hydrochlorothiazide, telmisartan/hydrochlorothiazide, telmisartan/amlodipine besilate/hydrochlorothiazide

Dose of HCTZ	The dose of HCTZ is the maximum dose in patients receiving HCTZ.
Ca antagonist	
Drugs described in the column for details on the use of other antihypertensive in the CRF that have a NHI drug code starting with any of the following 7-digit numbers:
 
2171022, 2171014, 2171019, 2171020, 2149019, 2149022, 2149043, 2149027, 2149034, 2149037, 2149038, 2171021, 2149035, 2149030, 2171006, 2149116, 2149114, 2149117, 2149118, 2149115, 2190101, 2190102, 2190103, 2190104, 2149120, 2149122
 
Generic name: amlodipine besilate, nifedipine, nisoldipine, nitrendipine, nicardipine hydrochloride, nilvadipine, azelnidipine, manidipine hydrochloride, efondipine hydrochloride ethanol, cilnidipine, aranidipine, benidipine hydrochloride, felodipine, barnidipine hydrochloride, diltiazem hydrochloride, candesartan cilexetil/amlodipine besilate, valsartan/amlodipine besilate, telmisartan/amlodipine besilate, irbesartan/amlodipine besilate, olmesartan medoxomil/azelnidipine, amlodipine besilate/atorvastatin calcium hydrate, valsartan/cilnidipine, telmisartan/amlodipine besilate/hydrochlorothiazide

Direct renin inhibitor	
Drugs described in the column for details on the use of other antihypertensive in the CRF that have a NHI drug code starting with the following 7-digit number:
 
2149047
 
Generic name: aliskiren fumarate

Aldosterone antagonist/potassium-sparing diuretic	
Drugs described in the column for details on the use of other antihypertensive in the CRF that have a NHI drug code starting with any of the following 7-digit numbers:
 
2133001, 2149045, 2133002
 
Generic name: spironolactone, eplerenone, triamterene

Aldosterone antagonist	Drugs described in the column for details on the use of other

Term	Definition
	
antihypertensive in the CRF that have a NHI drug code starting with any of the following 7-digit numbers:
 
2133001, 2149045,
 
Generic name: spironolactone, eplerenone

Potassium-sparing diuretic	
Drugs described in the column for details on the use of other antihypertensive in the CRF that have a NHI drug code starting with the following 7-digit number:
 
2133002
 
Generic name: triamterene

Diuretic	
Diuretics (thiazide and thiazide analogue diuretics) or potassium-sparing diuretics described in the column for details on the use of other antihypertensive in the CRF

Vasodilator	
Drugs described in the column for details on the use of other antihypertensive in the CRF that have a NHI drug code starting with the following 7-digit number:
 
2142004
 
Generic name: hydralazine hydrochloride

β -blocker	
Drugs described in the column for details on the use of other antihypertensive in the CRF that have a NHI drug code starting with any of the following 7-digit numbers:
 
2123011, 2123016, 2149700, 2149031, 2149010, 2123001, 2149029, 2123008, 2149014, 2149021, 2149028, 2123015, 2123005, 2149025, 2123009, 2149011
 
Generic name: atenolol, bisoprolol fumarate, bisoprolol, betaxolol hydrochloride, metoprolol tartrate, acebutolol hydrochloride, celiprolol hydrochloride, propranolol hydrochloride, nifradilol, tilisolol hydrochloride, nadolol, carteolol hydrochloride, pindolol

Central sympathetic inhibitor	
Drugs described in the column for details on the use of other antihypertensive in the CRF that have a NHI drug code starting with any of the following 7-digit numbers:
 
2149001, 2149017, 2145001
 
Generic name: clonidine hydrochloride, guanabenz acetate, methyldopa hydrate

$\alpha\beta$ -blocker	
Drugs described in the column for details on the use of other antihypertensive in the CRF that have a NHI drug code starting with any of the following 7-digit numbers:

Term	Definition
	2149032, 2149018, 2123014, 2149009, 2149036 Generic name: carvedilol, amosulalol hydrochloride, arotinolol hydrochloride, labetalol hydrochloride, bevantolol hydrochloride
α_1 -blocker	Drugs described in the column for details on the use of other antihypertensive in the CRF that have a NHI drug code starting with any of the following 7-digit numbers: 2149026, 2149015, 2149023, 2149002, 2149020 Generic name: doxazosin mesilate, bunazosin hydrochloride, terazosin hydrochloride hydrate, prazosin hydrochloride, urapidil
Fixed-dose combination: ARB + diuretic	Drugs described in the column for details on the use of other antihypertensive in the CRF that have a NHI drug code starting with any of the following 7-digit numbers: 2149110, 2149111, 2149112, 2149113, 2149119, 2149122 Generic name: losartan potassium/hydrochlorothiazide, candesartan cilexetil/hydrochlorothiazide, valsartan/hydrochlorothiazide, telmisartan/hydrochlorothiazide, irbesartan/trichlormethiazide, telmisartan/amlodipine besilate/hydrochlorothiazide
Fixed-dose combination: ARB + Ca antagonist	Drugs described in the column for details on the use of other antihypertensive in the CRF that have a NHI drug code starting with any of the following 7-digit numbers: 2149116, 2149114, 2149117, 2149118, 2149115, 2149120, 2149122 Generic name: candesartan cilexetil/amlodipine besilate, valsartan/amlodipine besilate, telmisartan/amlodipine besilate, irbesartan/amlodipine besilate, olmesartan medoxomil/azelnidipine, valsartan/cilnidipine, telmisartan/amlodipine besilate/hydrochlorothiazide
Fixed-dose combination: ARB + Ca antagonist + diuretic	Drugs described in the column for details on the use of other antihypertensive in the CRF that have a NHI drug code starting with the following 7-digit number: 2149122 Generic name: telmisartan/amlodipine besilate/hydrochlorothiazide
Fixed-dose combination: Ca antagonist + statin	Drugs described in the column for details on the use of other antihypertensive in the CRF that have a NHI drug code starting with any of the following 7-digit numbers: 2190101, 2190102, 2190103, 2190104 Generic name: amlodipine besilate/atorvastatin calcium hydrate
Other (antihypertensive)	Vasodilators, β -blockers, central sympathetic inhibitors, $\alpha\beta$ -blockers, and

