2.0 Objectives

To evaluate the safety and efficacy of long-term use of Zacras Combination Tablets in hypertensive patients in daily medical practice

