5.3.1 Occurrence of Adverse Events by Seriousness, Time of Onset, and Outcome

(1) Patients included in tabulation/analysis

Patients included in safety evaluation

(2) Data tabulated/analyzed

AEs will be categorized for each variable as described below, and the type of AE will be tabulated.

Variable	Category
Seriousness	Serious, non-serious
Time of onset	Days 1 to 180, Days 181 to 360, Day 361 or later
Outcome	Recovered, recovering, not recovered, recovered with sequelae, fatal, unknown

The type of AE will be tabulated as described below.

Variable	Data tabulated/analyzed
Number of patients	Number of patients who experienced an AE by SOC/PT
Number of AE	Number of reported AE by SOC/PT
Type of AE	
AEs will be classified by SOC and then tabulated by PT. For laboratory tests, AEs will be classified by SOC, then sorted by HLGT, and finally tabulated by PT.
 
AEs will be listed for SOC by SOC internationally agreed order and for PT in ascending order of PT code.
 
Multiple episodes of the same AE (PT) in the same patient will be tabulated by category as the total number of episodes (for instance, one episode of serious diarrhoea and one episode of non-serious diarrhoea in the same patient will be counted once in the respective categories).

(3) Table/figure number

Table 5.3-1

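### Undated and partially dated adverse events are set to their earliest possible day and then counted in the onset windows as if observed, so any such event can only move earlier

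*SAP*

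**What the plan says.** SAP 1.1 (Definitions, Time of onset) sets the formula: "Time of onset will be calculated as date of onset of AE (or ADR, etc.) - start date of treatment + 1". The start day is therefore Day 1. Incomplete dates are then resolved as follows.

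- No date at all: "If the year, month, and day of AE (or ADR, etc.) is unknown, the start date of treatment will be used for calculation", which gives Day 1.
- Year only: "If the month and day of AE (or ADR, etc.) are unknown, January 1 will be used for calculation". If the year is the one in which treatment began, the rule is different: the event "occurs in the same year as treatment is started, the month and day of starting treatment will be used for calculation", which again gives Day 1.
- Year and month only: "If the day of AE (or ADR, etc.) is unknown, 1 will be used for calculation", or the treatment start date if the event falls in the month in which treatment began.

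SAP 5.3.1 (adverse events) and 5.3.2 (adverse drug reactions) tabulate by the windows "Days 1 to 180, Days 181 to 360, Day 361 or later". Neither has a category for unknown onset, a mark for imputed dates or a sensitivity tabulation. In the same tables, outcome does have an unknown category. In the same definitions list, duration of disease is left missing when the diagnosis date is wholly unknown.

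Protocol 10.4.1 asks for adverse event incidence by time of onset, among other breakdowns. Protocol 2.0 states the objective: "To evaluate the safety and efficacy of long-term use of Zacras Combination Tablets in hypertensive patients in daily medical practice".

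**The concern.** Every one of these rules picks the earliest date compatible with the record. Sorting events into onset windows needs a rule whose error does not run in one direction. This one's error does: an imputed day is never later than the true day, so an event can pass from a later window to an earlier one but not back.

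Once an event is in the table, an imputed Day 1 cannot be told from an observed Day 1. Section 5.3 is the only part of the current SAP that resolves adverse events by time. In a long-term survey, a reader asking whether reactions emerge late in treatment will look there. If events with incomplete dates exist, some late ones will be counted as early and the reader will have no way to see it.

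**Working it through.** The plan states no figure on this point, so there is none to reproduce. The check applies the SAP rules to every possible case.

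**Inputs from the documents**
- Onset day = onset date − start date + 1 (SAP 1.1).
- Imputation rules as listed in SAP 1.1.
- Early window: Days 1 to 180 (SAP 5.3.1, 5.3.2). Late here means after Day 180.
- Enrolment from June 2014 to 31 January 2016 (Protocol 8.0).
- Follow-up to Day 361: SAP 1.1 sets the end of treatment at start + 360 days for patients still on treatment at 12 months.

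**Assumptions not in the documents**
- The first start date is 1 June 2014, and starts are uniform over the 610 days to 31 January 2016.
- True onset is uniform over Days 1 to 361.

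**One patient by hand.** Start 1 October, event dated only with the following year. 1 January is Day 93 (31 + 30 + 31 + 1), so the event is counted in Days 1 to 180. The record allows Days 93 to 361, which is 361 − 93 + 1 = 269 days. Of these, 180 − 93 + 1 = 88 are early and 361 − 180 = 181 are late.

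**A patient for whom the year-only rule does little.** Start 15 June: 1 January is Day 201, so an event dated with the following year stays late. Only late events still in the start year, Days 181 to 200, go to Day 1: 20 of 181 late days, or 11%. The switch is between a start on 5 July (1 January = Day 181) and one on 6 July (1 January = Day 180).

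**Enumeration.** 610 start dates × 181 late onset days = 110,410 late cases. The number counted in Days 1 to 180 is:

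| What is known of the date | Late cases counted as early | Share |
|---|---|---|
| Nothing | 110,410 | 100% |
| Year only | 87,874 | 79.6% |
| Year and month | 8,977 | 8.1% |

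Truly early cases moved late: 0 in all three rows. The year-only share depends strongly on the month of starting treatment. For 2015 starts it runs from 11% (June) to 100% (August to December).

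**Effect on the early share of events.** Let u be the share of events with no date, L the true late share, and let missingness be unrelated to onset time. The true early share is 1 − L. The tabulated early share is (1 − L) + u × L, so the shift is u × L.

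| u | L = 30% | L = 50% |
|---|---|---|
| 0% | 0 | 0 |
| 5% | 1.5 points | 2.5 points |
| 10% | 3 points | 5 points |
| 20% | 6 points | 10 points |

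The documents give neither u nor L; the values are illustrative.

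**The case against.** The strongest reply is that these rules are a fallback that may never be used. Onset date is a required item for each adverse event (Protocol 9.2.5), and the sponsor can request detail on serious events (Protocol 7.5). This stands: the documents give no share of incomplete dates, and at zero nothing changes. A reader might infer that the survey's tables do understate late onset. The documents do not support that; they support only that any incompletely dated late event may be counted as early.

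A reader might also infer that the plan will print a distorted early-to-late ratio, for example 55:45 in place of 50:50 with 10% of events undated. Section 5.3 prints counts of patients and events by system organ class and preferred term within each window, with no such ratio, no test and no comparison. A 50:50 split further assumes constant risk and everyone followed to Day 361. Adverse event collection ends at discontinuation (Protocol 9.2.5), and SAP 4.0 provides for treatment durations of 1 to 180 days. Fewer patients are then at risk late, so L may well be below 50%. For a patient whose observation ended by Day 180, counting an undated event as early is correct.

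Finally, time of onset is one descriptive breakdown among several, and the sample-size rationale (Protocol 3.2) centres on renal impairment, hepatic impairment and age 75 or over. That also stands and bears on severity. It does not remove the defect: where the rule applies, it can put an event in a window its record does not establish, without telling the reader.

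**Conclusion.** The point holds as a conditional one, and it is minor. The mechanism is certain from the text: earliest-date imputation feeds onset windows that have no unknown category and no flag, and the error runs one way. The figures of 100%, about 80% and about 8% rest on uniform start dates and uniform onset to Day 361, and the middle one varies widely with start month. The effect on the actual tables cannot be computed. It is zero if all dates are complete, and otherwise, for undated events, it is the undated share times the true late share.

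The reach is limited to the time-of-onset counts in Tables 5.3-1 and 5.3-2. Overall adverse event and reaction incidence (5.1), reaction incidence by factor (5.4) and the serious event tables (5.5) do not use onset day and are unaffected. A reader might take the point as a threat to the survey's safety conclusions in general; the documents do not support that.

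**What to change.** In SAP 1.1 and 5.3, assign an undated or partially dated event to an onset window only when every date its record allows, from treatment start to the end of that patient's observation, falls in that same window. Count all other such events in an added onset-unknown category in Tables 5.3-1 and 5.3-2, as those tables already do for outcome. Under this rule an undated event in a patient whose observation ended by Day 180 is still counted in Days 1 to 180.

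The start-date imputation need not be kept for another purpose: the current SAP has no on-treatment classification that uses onset day.

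The cost is a few lines of SAP wording and one added category in two tables, with no new data. The downside is that a few events appear as unknown. If the category is nearly empty, that itself shows the reader that the onset counts are sound.
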